9.7 Early phase safety monitoring

The Investigator will monitor adverse events in an ongoing manner and inform the Sponsor of any clinically relevant observations. Any required safety reviews will be made jointly between medically qualified personnel representing the Sponsor and Investigator. Such evaluations may occur verbally, but the outcome and key discussion points will be summarized in writing (e-mail) and made available to both Sponsor and all Investigator(s). Criteria pertaining to stopping the study/treatment or adapting the study design are presented above.

9.8 Monitoring hypoglycemia

Because hypoglycemia is a potential risk of LIK066 treatment, glucose levels will be measured when a subject experiences a clinically symptomatic hypoglycemia. If a confirmed glucose level is <56 mg/dL by repeated measurement, study treatment will be discontinued and the patient will be treated by the clinical staff according to standard of care for hypoglycemia.

During the course of the study, if any patient experiences symptoms of hypoglycemia (shakiness, nervousness, hunger, nausea, palpitations, dizziness, or confusion), they will be instructed to seek immediate medical evaluation and treatment.

[figure not shown]
9.9 Monitoring orthostatic hypotension

Because orthostatic hypotension is a potential risk of LIK066 treatment, orthostatic blood pressure readings will be recorded throughout the study as shown in the [Assessment schedule](#).

Any patient with clinically significant symptomatic orthostasis (more than 20 mmHg drop in systolic or 10 mmHg drop in diastolic blood pressure and increase in heart rate >20 bpm) will have the study treatment placed on hold. In addition, individuals with orthostasis will be treated with volume replacement according to standard of care (refer to [Section 7.2](#) (Discontinuation of study treatment)).

9.10 Monitoring ketoacidosis

In rare cases, SGLT-2 inhibitors can lead to ketoacidosis. Therefore, investigators must pay close attention for any signs of ketoacidosis. Signs and symptoms of ketoacidosis may include deep and rapid breathing, nausea, vomiting, severe abdominal pain, confusion, unusual fatigue or sleepiness, and coma. All signs and/or symptoms and results from relevant laboratory tests must be reported on the AE eCRF. If ketoacidosis is confirmed, the study treatment should be discontinued as per [Section 7.2](#) (Discontinuation of study treatment) and appropriate measures must be taken to correct the acidosis and monitor glucose levels according to standard of care.

Every case of ketoacidosis must be reported to the Ketoacidosis Adjudication Committee (see [Section 10.5](#)).

10 Data review and database management

10.1 Site monitoring

Before study initiation, at a site initiation visit or at an investigator's meeting, a Novartis representative will review the protocol and CRFs with the investigators and their staff. During the study Novartis employs several methods of ensuring protocol and GCP compliance and the quality/integrity of the sites' data. The monitor will visit the site to check the completeness of subject records, the accuracy of entries on the CRFs, the adherence to the protocol and to Good Clinical Practice, the progress of enrollment, and ensure that study drug is being stored, dispensed, and accounted for according to specifications. Key study personnel must be available to assist the monitor during these visits.

The investigator must maintain source documents for each subject in the study, consisting of case and visit notes (hospital or clinic medical records) containing demographic and medical information, laboratory data, electrocardiograms, and the results of any other tests or assessments. All information on CRFs must be traceable to these source documents in the subject's file. The investigator must also keep the original informed consent form signed by the subject (a signed copy is given to the subject).

The investigator must give the monitor access to all relevant source documents to confirm their consistency with the CRF entries. Novartis monitoring standards require full verification for the presence of informed consent, adherence to the eligibility criteria, documentation of SAEs, and the recording of data that will be used for all primary and safety variables. Additional checks of the consistency of the source data with the CRFs are performed according to the study-specific monitoring plan. No information in source documents about the identity of the subjects will be disclosed.

10.2 Data collection

Designated investigator staff will enter the data required by the protocol into the Electronic Case Report Forms using fully validated software that conforms to 21 CFR Part 11 requirements. Designated investigator site staff will not be given access to the EDC system until they have been trained. Automatic validation programs check for data discrepancies and, by generating appropriate error messages, allow the data to be confirmed or corrected before transfer of the data to Novartis or the CRO working on behalf of Novartis. The Investigator must certify that the data entered into the Electronic Case Report Forms are complete and accurate. After database lock, the investigator will receive copies of the subject data for archiving at the investigational site.

Data not requiring a separate written record will be defined in the Site Operations Manual and [Assessment schedule](#) and can be recorded directly on the CRFs. All other data captured for this study will have an external originating source (either written or electronic) with the CRF not being considered as source.

All data should be recorded, handled and stored in a way that allows its accurate reporting, interpretation and verification.

10.3 Database management and quality control

[figure not shown]
Novartis staff or CRO working on behalf of Novartis review the data entered into the CRFs by investigational staff for completeness and accuracy and instruct the site personnel to make any required corrections or additions. Queries are sent to the investigational site using an electronic data query. Designated investigator site staff is required to respond to the query and confirm or correct the data. If the electronic query system is not used, a paper Data Query Form will be faxed to the site. Site personnel will complete and sign the faxed copy and fax it back to Novartis staff or CRO working on behalf of Novartis who will make the correction to the database. The signed copy of the Data Query Form is kept at the investigator site.

Concomitant medications entered into the database will be coded using the WHO Drug Reference List, which employs the Anatomical Therapeutic Chemical classification system. Medical history/current medical conditions and adverse events will be coded using the Medical dictionary for regulatory activities (MedDRA) terminology.

Laboratory samples will be processed centrally and the results will be sent electronically to Novartis (or a designated CRO).

ECG readings will be processed locally and the results will be sent electronically to Novartis (or a designated CRO).

The occurrence of any protocol deviations will be determined. After these actions have been completed and the database has been declared to be complete and accurate, it will be locked and the treatment codes will be unblinded and made available for data analysis. Any changes to the database after that time can only be made by joint written agreement between the COAR Analytics NIBR Franchise Head and the relevant NIBR TA Head.

10.4 Data Monitoring Committee

Not applicable.

10.5 Adjudication Committee

An Adjudication Committee for monitoring ketoacidosis will be established to assess suspected cases of ketoacidosis as described in the SOM.

11 Data analysis

All data analyses will be performed by study part.

11.1 Analysis sets

For all analysis sets, subjects will be analyzed according to the study treatment(s) received.

The safety analysis set will include all subjects that received any study drug.

[REDACTED]

The PD analysis set will include all subjects with available PD data and no protocol deviations with relevant impact on PD data.

11.2 Subject demographics and other baseline characteristics

All data for background and demographic variables will be listed by treatment sequence and subject. Summary statistics will be provided for all subjects, as well as for each treatment sequence.

Relevant medical history, current medical conditions, results of laboratory screens, drug tests and any other relevant information will be listed by treatment sequence and subject.

11.3 Treatments

Data for study drug administration and concomitant therapies will be listed by treatment sequence and subject.

11.4 Analysis of the primary variable(s)

11.4.1 Variable(s)

The primary endpoint will be the number of episodes of diarrhea per day. It is defined as the total number of stools with a BSC score of 6 or 7 per day.

11.4.2 Statistical model, hypothesis, and method of analysis

The primary analysis will be performed by study part. The daily number of diarrhea will be analyzed using a negative binomial mixed effects model with fixed effects of period, treatment, day, the period-by-day interaction, and the treatment-by-day interaction, and a random subject effect. An unstructured covariance matrix will be specified for the repeated observations on a subject within the same period. The least-squares mean and associated 80% CI for the number of diarrhea episodes per day for each treatment, and the estimated mean difference between each treatment, the p-value, and corresponding two-sided 80% CI, will be extracted from the model for each day, and summarized by a table and a line chart. Conclusions from the analysis will be based on treatment differences from all 3 days, collectively.

[REDACTED]

11.4.3 Handling of missing values/censoring/discontinuations

The primary analysis will be performed on all available data. There will be no imputation of missing data.

11.4.4 Sensitivity analyses

As a sensitivity analysis, the interaction between treatment and day will be assessed, and if non-significant, the results from the 3 days will be averaged and corresponding model-based quantities extracted.

Covariates such as baseline number of diarrhea may be included in the model when appropriate.

The model assumption of negative binomial distribution will be examined, especially if over-dispersion (i.e. variance>mean) exists. If the data doesn't fit negative binomial distribution or over-dispersion doesn't exist, other models such as Poisson regression will be explored.

The model assumption of no first-order carry-over effect may be evaluated by incorporating first-order carry-over effects into the above statistical model, and performing a type 3 test for the first-order carry-over effect.

11.5 Analysis of secondary variable(s)

11.5.1 Efficacy / Pharmacodynamics

The three-day total number of episodes of diarrhea per period will be summarized by treatment, and analyzed using a negative binomial model with fixed effects of subject, period and diet. The least-squares mean and associated 80% CI for the three-day total number of diarrhea episodes per period for each treatment, and the estimated mean difference between each treatment, the p-value, and corresponding two-sided 80% CI, will be extracted from the model, and summarized by a table and a line chart.

The model assumption of no first-order carry-over effect and the negative-binomial distribution may be evaluated in a similar fashion as the primary endpoint.

Other secondary endpoints include average consistency with Bristol stool chart, average stool pH, average stool weight over each 24 hour collection period. They will be summarized by treatment, and analyzed by a linear mixed model with fixed effects of subject, period, treatment, and baseline measurement. The least-squares mean and associated 80% CI for each treatment, and the estimated mean difference between each treatment, the p-value, and corresponding two-sided 80% CI, will be extracted from the model, and summarized by a table and a line chart.

11.5.2 Safety

Vital signs

All vital signs data will be listed by treatment sequence, subject, and visit/time and if ranges are available abnormalities (and relevant orthostatic changes) will be flagged. Summary statistics for both observed values and change from baseline will be provided by treatment and visit.

ECG evaluations

All ECG data will be listed by treatment sequence, subject and visit/time, abnormalities will be flagged. Summary statistics for both observed values and change from baseline will be provided by treatment and visit.

Clinical laboratory evaluations

All laboratory data will be listed by treatment sequence, subject, and visit/time and if normal ranges are available abnormalities will be flagged. Summary statistics will be provided by treatment and visit.

Adverse events

All information obtained on adverse events will be displayed by treatment sequence and subject.

The number and percentage of subjects with adverse events will be tabulated by body system and preferred term with a breakdown by treatment. An adverse event starting in one period/epoch and continuing into the next period/epoch is counted only in the onset period. A subject with multiple adverse events within a body system and treatment period/epoch is only counted once towards the total of this body system and treatment.

Other safety evaluations

Immunogenicity

[figure not shown]
Not applicable.

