9.1 Adverse events

[figure not shown]
An adverse event (AE) is any untoward medical occurrence (i.e., any unfavorable and unintended sign [including abnormal laboratory findings], symptom or disease) in a subject or clinical investigation subject *after providing written informed consent* for participation in the study until the end of study visit. Therefore, an AE may or may not be temporally or causally associated with the use of a medicinal (investigational) product.

In addition, all reports of intentional misuse and abuse of the study treatment are also considered an adverse event irrespective if a clinical event has occurred. See [Section 9.5](#) for an overview of the reporting requirements.

The occurrence of adverse events must be sought by non-directive questioning of the subject at each visit during the study. Adverse events also may be detected when they are volunteered by the subject during or between visits or through physical examination finding, laboratory test finding, or other assessments.

Abnormal laboratory values or test results constitute adverse events only if they fulfill at least one of the following criteria:

- they induce clinical signs or symptoms,
- they are considered clinically significant,
- they require therapy.

Clinically significant abnormal laboratory values or test results should be identified through a review of values outside of normal ranges/clinically notable ranges, significant changes from baseline or the previous visit, or values which are considered to be non-typical in subjects with underlying disease. Investigators have the responsibility for managing the safety of individual subject and identifying adverse events. Alert ranges for liver and kidney related events are included in [Appendix 1](#) and [Appendix 2](#), respectively.

Adverse events must be recorded on the Adverse Events CRF under the signs, symptoms or diagnosis associated with them, and accompanied by the following information:

1. the severity grade
 - mild: usually transient in nature and generally not interfering with normal activities
 - moderate: sufficiently discomforting to interfere with normal activities
 - severe: prevents normal activities
2. its relationship to the study treatment
 - Yes or
 - No
3. its duration (start and end dates) or if the event is ongoing an outcome of not recovered/not resolved must be reported.

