4. whether it constitutes a SAE (see [Section 9.2](#) for definition of SAE) and which seriousness criteria have been met
5. Action taken regarding investigational treatment.

All adverse events must be treated appropriately. Treatment may include one or more of the following:

- no action taken (e.g. further observation only)
- investigational treatment dosage increased/reduced
- investigational treatment interrupted/withdrawn
- concomitant medication or non-drug therapy given
- hospitalization/prolonged hospitalization (see [Section 9.2](#) for definition of SAE)

6. its outcome (not recovered/not resolved; recovered/resolved; recovering/resolving, recovered/resolved with sequelae; fatal; or unknown).

Information about common side effects already known about the investigational drug can be found in the Investigator's Brochure (IB). Once an adverse event is detected, it must be followed until its resolution or until it is judged to be permanent, and assessment should be made at each visit (or more frequently, if necessary) of any changes in severity, the suspected relationship to the investigational drug, the interventions required to treat it, and the outcome.

The investigator must also instruct each subject to report any new adverse event (beyond the protocol observation period) that the subject, or the subject's personal physician, believes might reasonably be related to study treatment. This information must be recorded in the investigator's source documents; however, if the AE meets the criteria of an SAE, it must be reported to Novartis.

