9.2 Serious adverse event reporting

9.2.1 Definition of SAE

An SAE is defined as any adverse event (appearance of (or worsening of any pre-existing) undesirable sign(s), symptom(s) or medical conditions(s)) which meets any one of the following criteria:

- is fatal or life-threatening
- results in persistent or significant disability/incapacity
- constitutes a congenital anomaly/birth defect
- requires inpatient hospitalization or prolongation of existing hospitalization, unless hospitalization is for:
 - treatment on an emergency outpatient basis for an event not fulfilling any of the definitions of a SAE given above and not resulting in hospital admission
 - social reasons and respite care in the absence of any deterioration in the subject's general condition
- is medically significant, e.g. defined as an event that jeopardizes the subject or may require medical or surgical intervention.

All malignant neoplasms will be assessed as serious under "medically significant" if other seriousness criteria are not met.

Life-threatening in the context of a SAE refers to a reaction in which the subject was at risk of death at the time of the reaction; it does not refer to a reaction that hypothetically might have caused death if it were more severe (see Annex IV, ICH-E2D Guideline).

[figure not shown]
Medical and scientific judgment should be exercised in deciding whether other situations should be considered serious reactions, such as important medical events that might not be immediately life threatening or result in death or hospitalization but might jeopardize the subject or might require intervention to prevent one of the other outcomes listed above. Examples of such events are intensive treatment in an emergency room or at home for allergic bronchospasm, blood dyscrasias or convulsions that do not result in hospitalization or development of dependency or abuse (see Annex IV, ICH-E2D Guideline).

Any suspected transmission via a medicinal product of an infectious agent is also considered a serious adverse reaction.

All AEs (serious and non-serious) are captured on the CRF; SAEs also require individual reporting to Novartis Drug Safety & Epidemiology (DS&E) as per [Section 9.2.2](#).

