7.2 Descriptive analyses

Subject demographics and other baseline characteristics

All data for background and demographic variables will be listed by treatment sequence and subjects in the safety analysis set. Summary statistics will be provided for all subjects in the safety analysis dataset, as well as for each treatment sequence.

Relevant medical history, current medical conditions, results of laboratory screens, drug tests and any other relevant information will be listed by treatment sequence and subject.

Subject disposition (frequency of completion/discontinuation and reasons for early discontinuation) will be summarized by epoch and treatment sequence.

Treatment

Data for study drug administration and meal/supplement dosing and concomitant therapies will be listed by treatment sequence and subject. Number of dose administration will be summarized by treatment.

Vital signs

All vital signs data will be listed by treatment sequence, subject, and visit/time and if ranges are available abnormalities (and relevant orthostatic changes) will be flagged. Summary statistics will be provided by treatment and visit/time.

ECG evaluations

All ECG data will be listed by treatment, subject and visit/time, abnormalities will be flagged. Summary statistics will be provided by treatment and visit/time.

Clinical laboratory evaluations

All laboratory data will be listed by treatment, subject, and visit/time and if normal ranges are available abnormalities will be flagged. A separate listing is provided presenting all parameters in a subject with any abnormal values. Summary statistics will be provided by treatment and visit/time.

Adverse events (AEs)

All information obtained on adverse events will be listed by treatment sequence and subject.

The number and percentage of subjects with adverse events will be tabulated by body system and preferred term with a breakdown by treatment. An adverse event starting in one period/epoch and continuing into the next period/epoch is counted only in the onset period. A subject with multiple adverse events within a body system and treatment period/epoch is only counted once towards the total of this body system and treatment. If AE dates are needed to assign onset period and the dates are missing, AE date will be imputed by the following rule: if year is missing there will be no imputation of date. Otherwise missing month will be imputed by January, and missing day will be imputed by 1st.

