Serious adverse events and adverse events leading to early discontinuation will be listed by treatment sequence and subject.

Adverse events leading to death will be listed by treatment sequence and subject.

For the legal requirements of ClinicalTrials.gov and EudraCT, two required tables on on-treatment/treatment emergent adverse events which are not serious adverse events with an incidence greater than 1% and on on-treatment/treatment emergent serious adverse events and SAE suspected to be related to study treatment will be provided by system organ class and preferred term on the safety set population.

If for a same patient, several consecutive AEs (irrespective of study treatment causality, seriousness and severity) occurred with the same SOC and PT:

- a single occurrence will be counted if there is ≤ 1 day gap between the end date of the preceding AE and the start date of the consecutive AE
- more than one occurrence will be counted if there is > 1 day gap between the end date of the preceding AE and the start date of the consecutive AE.

For occurrence, the presence of at least one SAE / SAE suspected to be related to study treatment / non SAE has to be checked in a block e.g., among AE's in a ≤ 1 day gap block, if at least one SAE is occurring, then one occurrence is calculated for that SAE.

[figure not shown]
The number of deaths resulting from SAEs suspected to be related to study treatment and SAEs irrespective of study treatment relationship will be provided by SOC and PT.

[figure not shown]
Immunogenicity

Not applicable

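### Adverse events are counted only where they began, so a worsening kept on the original record is not counted under the treatment on which it occurred (minor; by-treatment AE tables only)

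*Protocol*

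**What the plan says.** Protocol 11.5.2 describes the main safety table: "The number and percentage of subjects with adverse events will be tabulated by body system and preferred term with a breakdown by treatment". It then says how continuing events are placed: "An adverse event starting in one period/epoch and continuing into the next period/epoch is counted only in the onset period". SAP 7.2 repeats the rule. It places events by AE date, as its imputation rule shows: "If AE dates are needed to assign onset period and the dates are missing, AE date will be imputed by the following rule". Neither section mentions a date of severity change, and neither describes a breakdown by severity.

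On collection, protocol 9.1 counts an untoward occurrence as an AE if it arises "after providing written informed consent", and 8.4 limits medical history to the time before consent is signed. Each AE record carries a severity grade and start and end dates. For open events, 9.1 says "Once an adverse event is detected, it must be followed until its resolution or until it is judged to be permanent", with assessment at each visit "of any changes in severity, the suspected relationship to the investigational drug, the interventions required to treat it, and the outcome".

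The SAE definition in 9.2.1 covers the "appearance of (or worsening of any pre-existing) undesirable sign(s), symptom(s) or medical conditions(s". For the registry tables, SAP 7.2 uses the terms on-treatment and treatment emergent without defining them. There it merges records at most one day apart, "irrespective of study treatment causality, seriousness and severity) occurred with the same SOC and PT".

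**The concern.** Sites are told to watch for changes in severity, but no readable counting rule uses what they see. In a crossover the column in which an event appears is the comparison, and onset alone decides that column. Two kinds of event can be left out of the column for the treatment on which they worsened:

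- **Pre-dose onset.** Bloating that starts during run-in and worsens after the first LIK066 dose has its onset in an epoch with no treatment.
- **Onset under an earlier treatment.** A symptom that starts in one treatment period, or in the washout after it, and worsens under the next meal or supplement stays with the earlier epoch.

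At stake is how completely the descriptive by-treatment AE table shows on-drug worsening, in a trial whose subject is gastrointestinal tolerability.

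**Working it through.** The plan gives no figure to reproduce. The check follows an event through the rules and then asks how far the rule reaches.

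**Step 1: which column an event enters, if a worsening stays on the original record**

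| Onset | Worsens | Where the rule counts it | Counted under the treatment on which it worsened? |
|---|---|---|---|
| Screening or run-in (to Day -1) | Day 1 onward | Pre-treatment epoch | No; no treatment column |
| Treatment days of Period 1 (Days 1 to 3) | Day 9 onward | Period 1 treatment | No |
| Washout (Days 4 to 8) | Day 9 onward | Period 1 treatment, because Table 8-1 places Days 4 to 8 in the Treatment Period 1 epoch | No |

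Table 8-1 likewise places Days 12 to 16 in the Treatment Period 2 epoch. The protocol glossary also gives washout as an example of a period. On that reading the third row would fall under no treatment, and the last column would not change.

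**Step 2: the same events, if the site opens a new record at the worsening**

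The new record has its own start date in the later period, so the by-treatment table counts it there. The result therefore depends on recording practice. Section 9.1 does not settle this, and 8.6 refers methods of recording safety assessments to the Site Operations Manual, which is not among the documents.

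**Step 3: the time an event must last**

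- Run-in to Period 1: Day -1 is followed directly by Day 1, so there is no gap. All of the approximately 24 subjects per part make this transition.
- Onset on the last dosing day: it must persist from Day 3 to Day 9, or from Day 11 to Day 17, which is 6 days in each case (9 − 3 = 6; 17 − 11 = 6).
- Onset on the last washout day: Day 8 to Day 9, or Day 16 to Day 17, which is 1 day.
- In Table 6-1 each treatment comes first in one of three sequences of 8, so 2 × 8 = 16 of 24 subjects per part take it after another LIK066 treatment. This counts opportunities and says nothing about frequency.
- For diarrhea itself, protocol 3.2 reports 1 of 40 patients affected on the day after the last 50 mg qd dose (1/40 = 2.5%), so carry-over into the next period should be rare.

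**Step 4: size per event**

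Assume that the denominator is the number of subjects given the treatment. One uncounted subject lowers that treatment's percentage by 1/24 = 4.2 points. With the 15 completers per part in the sample size calculation (3 × 5), it would be 1/15 = 6.7 points. That is an extreme, because the safety set includes everyone dosed and section 4 expects at least 36 completers in all (36/2 = 18 per part if evenly split; 1/18 = 5.6 points). A table row changes only if the subject has no other AE in that row under the same treatment.

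**Step 5: the registry tables**

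Opening a new record may not help here. Two same-term records at most one day apart become one occurrence whatever their severity, and no readable text stops this at a period boundary. The merging rule is stated for these tables only.

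**The case against.** The strongest reply is that onset-based counting is a clear, pre-specified convention, stated identically in both documents, for descriptive tables in a non-confirmatory study. If worsening is itself an event, as 9.2.1 allows, it has its own onset and the rule counts it in the later period. On that view the documents do not conflict and only a recording instruction is missing. This largely stands: the convention is sound in itself, and the gap is its silence on worsening.

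A reader might infer more, and the documents do not support it:

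- *Worsened events are never counted.* That depends on recording guidance that cannot be seen. All AE information is also listed by sequence and subject, SAEs and AEs leading to discontinuation are listed separately, and a merged block containing an SAE is still counted as an SAE.
- *The AE table is the only treatment comparison for the supplement risks.* SAP 6.1.3 and 6.2.3 model bowel movements and average stool consistency by treatment, both of which bear on constipation. Other symptoms are recorded at each bowel movement, and redacted sections may analyse them.
- *Differences between treatments are pulled toward zero.* That would require later worsenings to concentrate on the less tolerable treatment, which nothing shows. Run-in events worsening in Period 1 meet treatments randomized 1:1:1.
- *Events are moved from one treatment to another.* The event did begin in the earlier period and belongs there. What may be missing is a second count.

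**Conclusion.** The point holds in a limited form. As written, the rule can undercount on-drug worsening in the by-treatment AE table wherever a worsening stays on the original record. The run-in to Period 1 transition is the most exposed, because it has no gap and every subject passes through it. The between-treatment case should be uncommon, since an event must last through some or all of the washout and then worsen.

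The size is about 4 points in a treatment's AE percentage per uncounted subject, assuming 24 subjects in the denominator. The number of such subjects cannot be estimated from the documents. The primary analysis counts BSC 6 or 7 stools per day and does not use this rule. This is a minor clarification of the safety tables.

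**What to change.** Keep the onset rule and add to protocol 11.5.2 and SAP 7.2:

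> An AE that continues into a later period is counted in its onset period. If its severity grade increases, or it becomes serious, on or after the first dose of that later period, it is also counted under the treatment of that period. This includes AEs that began before Day 1.

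Then make three matching changes:

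1. Define treatment emergent in the SAP in the same terms (new onset, or increased severity or seriousness, on or after a period's first dose) and use it in the registry tables.
2. State that the one-day merging rule does not join records across treatment periods.
3. In the CRF completion instructions, have sites either date a change in severity or open a new record when it occurs.

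The cost is a few sentences and one CRF instruction, with no new assessments because 9.1 already requires severity changes to be followed. The one small downside is that some AE percentages become slightly higher, because a subject can count for the same event under more than one treatment; a table footnote should say so.
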